4.2.5 Facioscapulohumeral Muscular Dystrophy Health Index (FSHD-HI)

The FSHD-HI data will be collected at at Week 1, every 3 months (Week 12, 24, etc), 1-Week Post-treatment Follow-up, and 12-Week Post-treatment Follow-up. The subscales and total score will be considered as continuous data. There are 14 subscales: Shoulder and Arm Function, Mobility, Fatigue, Cognitive Function, Activity Limitation, Core Strength and Function, Gastrointestinal Function, Social Performance, Body Image, Hand and Finger Function, Social Satisfaction, Pain, Emotional Health, and Communication. Each subscale contains a set number of questions. Some subscales have more questions than others. Each question within a specific FSHD-HI subscale measures a similar concept.

The scoring of FSHD-HI data will be managed by aTyr. Upon completion, the scores will be transferred to PRA for analysis and display. For each subject, fifteen scores are generated: the total FSHD-HI score and a score for each of the 14 subscales. The total FSHD-HI score is a composite of the 14-subscale scores weighted based on the average importance of the subscale. The average importance is based on patient input from a prior large-scale survey study of FSHD participants. The score for each subscale and the total FSHD-HI ranges from 0 to 100 with 100 representing the highest disease burden and 0 representing no disease burden.

4.3 Pharmacokinetic, Biomarker, and Genetic Data

Blood samples will be collected throughout the study for PK, biomarker, and genetic analysis. The analysis of these variables will be managed by aTyr. Specifically, variables that will not be summarized or listed as part of this SAP include the following:

- Serum ATYR1940 concentrations and pharmacokinetic variables
- Serum human histidyl-tRNA synthetase (HARS)
- Biomarkers listed in the protocol and any additional biomarkers from future analysis
- Immunophenotyping in peripheral blood mononuclear cells (PBMCs)
- *Ex vivo* culturing for FSHD-related immune protein release in PBMCs

5.0 Analysis Populations

Two Safety populations will be used: Safety Population 006 and Safety Population Cumulative.

5.1 Safety Population 006

The Safety population 006 will include all patients who have received at least 1 full or partial dose of ATYR1940 in the 006 study and have a postinfusion safety observation since enrolled in parent studies. The Safety population 006 will include data from the 006 study only.

5.2 Safety Population Cumulative

The Safety population cumulative will include the same patients as above, but it will include cumulative data from both the parent studies and the 006 study.

6.0 Definitions

Age

Age will be recorded on the CRF and not derived for this study.

Baseline

Baseline is defined as the baseline in the parent study.

Analyses of changes from pre-infusion to post-infusion (i.e., vital signs, and ECG) will use pre-infusion as well, when applicable. Post baseline values for tabulations will exclude unscheduled visit values; however, unscheduled visit values will be included in listings.

Change from Baseline

Change from baseline (CFB) will be calculated as (post-baseline – baseline). CFB will be calculated for patients with both a baseline and post-baseline value as applicable. Percent CFB will be calculated as (CFB/baseline)*100, where applicable.

If a baseline value has not been recorded for a parameter, then CFB will not be calculated for that parameter. Patients with missing CFB values will be excluded from analyses in which CFB is the endpoint.

Change from pre-infusion

Change from pre-infusion will be calculated as (post-infusion – pre-infusion). Change from pre-infusion will be calculated for patients with both pre-infusion and post-infusion values, as applicable. No imputation will be done for missing values.

Completion of study

A patient will be considered completed in the study when an End of Study CRF page indicates a completion date.

Concomitant medications

Concomitant medications are defined as any medications taken on or after the date of first date of infusion in the parent study. This includes medications that are ongoing at the time of first infusion.

Discontinuation of study

A patient will be considered discontinued from the study when an End of Study CRF page is completed indicating primary reason for discontinuation.

Prior medication

Prior medications are defined as any medications with start and stop dates prior to the date of first date of infusion in the parent study or an ongoing medications with a start date prior to first date of infusion in the parent study.

Protocol deviation

Potential planned or unplanned protocol deviations noted during clinical monitoring will be documented by category (i.e., inclusion criteria, exclusion criteria, study drug, safety assessment, lab/endpoint data, visit window, informed consent, prohibited co-medication, overdose/misuse, and other). All deviations will be reviewed, categorized, designated important or not important, and finalized prior to database lock according to the Protocol Deviation Guidance document. Important protocol deviations will be defined as those potentially impacting safety, immunogenicity, or PK/PD assessments.

Relationship to study treatment

AEs related to study treatment will be defined as those entered as possibly, likely, or definitely. None and unlikely will be considered not related to study treatment. If relationship is missing, then the AE will be considered as related to study treatment.

Study day

Study day is defined relative to the date of the first infusion (Week 1) in the current study. For assessments that occur after this visit date, study day is calculated as (assessment date – first infusion date + 1). For assessments that occur prior to first infusion date, study day will be calculated as (assessment date – first infusion date); there is no Study Day 0.

Treatment-emergent adverse event

An AE will be considered to be a treatment-emergent AE (TEAE) for the current study if the AE begins on or after parent study Week 13 visit (Week 13 Day 3 visit for study 004) through the 12-week post-treatment follow-up visit in the current study.

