- 1 Week 1 in the current study (ESW1) is equivalent to Week 14 in the parent study (PSW14). The Week 1 column in this table reflects assessments that are to be performed at ESW1 (cells with heavy weight borders) in addition to those performed at PSW14 (cells with regular weight borders), as indicated in the parent study protocol. All PSWeek 14/ESWeek 1 assessments are to be completed and eligibility is to be confirmed before the first ATYR1940 dose in the current study at ESW1.
- 2 A maximum duration of 3 weeks is permissible between the last ATYR1940 dose in the parent study (i.e., at Week 13) and the first ATYR1940 dose in the current study (at ESW1). A window >3 weeks may be permissible on a case-by-case basis, if required due to administrative reasons, after consultation with the Medical Monitor.
- 3 If there is >1 week (+3 days) between the last ATYR1940 dose in the parent study and the first ATYR1940 dose in the current study, the assessments indicated are to be repeated within 7 days before ESW1.
- 4 For scheduling purposes, a ±3-day window is permissible around ATYR1940 infusion; however, each ATYR1940 dose must be separated by at least 5 days and no more than 9 days and only 1 dose may be administered within a given study week; if a patient's scheduled visit day is changed in a given week (e.g., changed from Tuesday to Thursday), then subsequent weekly visits may be accordingly adjusted (e.g., Thursdays) or may revert back to the original schedule (e.g., Tuesdays), provided ATYR1940 is administered according to the timeframes specified. For the every 12-week and 6-month visits, a ±5-day window is permissible.
- 5 Weight is to be re-measured any time the Investigator suspects the patient has experienced a notable change in weight (±10%) and the ATYR1940 dose recalculated.

- 6 Vital signs are to be measured on weekly dosing days pre-infusion; every 30 minutes (± 5 minutes) during the infusion; at the end of the infusion (± 5 minutes); at 30 minutes (± 5 minutes) after the end of infusion; and at additional time points as clinically indicated. Vital signs also must be measured within 7 days before ATYR1940 administration at ESW1. (On weekly dosing days, post-infusion vital sign measurements also will be collected before blood sample collection.) In addition, vital signs are to be measured in the event of a generalized IRR (see Section 8.5.9.4).
- 7 To be performed every 3 months (± 1 week).

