8.5.10.2. Adverse Event Assessment

All AEs will be collected and recorded in this study from the time of the first ATYR1940 dose in this study through the EOS visit, or after the end of the study, if thought to be related to study drug. (AEs occurring through 30 days after the last study drug dose in the parent study and those occurring >30 days after the last study drug dose in the parent study that are considered by the Investigator to be study drug-related are to be reported in the parent study.) This includes AEs the patient reports spontaneously, those observed by the Investigator, and those elicited by the Investigator in response to open-ended questions during scheduled study center visits. Furthermore, all AEs that presented in the parent study that are ongoing at Week 1 in the current study will be recorded as such.

Each AE is to be assessed by the Investigator with regard to the following categories.

Serious/Non-Serious

AEs that meet the criteria specified in Section [8.5.10.1.3](#) are to be considered serious.

Relationship to Study Drug

The relationship of each AE to ATYR1940 is to be assessed by the Investigator according to categories in [Table 8](#).

Table 8: Criteria for Determination of Adverse Event Relationship to Study Drug

AE (is):	Relationship between ATYR1940 and AE:				
	Category				
	None	Unlikely	Possibly	Likely	Definitely
Clearly the result of an external factor	Yes	No	No	No	No
Probably/possibly the result of another factor	No	Yes	Yes	No	No
Has a chronological relationship with the time of administration and/or represents a known reaction to Study Drug	No	No	Yes	Yes	Yes
Disappears or decreases after discontinuation of the Study Drug	NA	NA	NA	Yes	Yes
Recurr on renewed administration (re-challenge)	No	No	NA	NA	Yes or NA**

** A re-challenge is not required; if done, re-challenge would be expected to be positive.

NA Not applicable

Intensity

The intensity of each AE is to be assessed by the Investigator according to the NCI CTCAE, version 4.03. If the AE is not included in the NCI CTCAE, version 4.03, then the Investigator is to determine the intensity of the AE according to the following criteria:

- Mild (Grade 1): Asymptomatic or mild symptoms: clinical or diagnostic observations only; intervention not indicated.
- Moderate (Grade 2): Minimal, local, or non-invasive intervention indicated; limiting age-appropriate instrumental activities of daily living.

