9.2.8. Safety Analysis

9.2.9. Safety and Immunogenicity Analyses

Safety evaluations will be based on the incidence, type, and intensity of AEs, and changes from baseline in safety laboratory tests, ECG findings, vital signs measurements, PFTs, and pulse oximetry. Immunogenicity will be assessed based on the incidence of infusion site reactions, ADA titers, changes in Jo-1 and ADA titers over time, as appropriate, as well as changes from baseline over time in immune-based laboratory tests, including, for example, tryptase, complement factors, and cytokines. Safety variables will be tabulated and presented for all patients who receive any amount of study drug and have follow-up safety data. Tabulations will be presented for safety data overall and separately for the parent and extension studies.

AEs will be coded using the current version of the Medical Dictionary for Regulatory Activities (MedDRA) for purposes of summarization. The overall incidence of AEs occurring during the study will be summarized by MedDRA system organ class and preferred term. The incidence of TEAEs also will be summarized by system organ class

and preferred term. For the purpose of analysis, a TEAE is defined as any AE that occurs after administration of the first dose of ATYR1940 through the 12-week posttreatment follow-up visit, or any event that is present at baseline, but worsens in intensity or is subsequently considered drug-related by the Investigator. Severe TEAEs, SAEs, and discontinuation rates of study therapy due to TEAEs also will be summarized.

Events that are considered related to treatment (possibly, likely, or definitely drug-related) will also be tabulated. A tabulation will also be provided that enumerates TEAEs by maximum severity. Deaths, SAEs, and TEAEs resulting in study discontinuation will be tabulated, if warranted by the data.

All AEs occurring on study will be listed in by-patient data listings.

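### The SAP opens the current-study TEAE window at the last parent-study dose, omits the protocol's worsening limb, gives no TEAE rule for the pooled block, and declares none of this

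*SAP*

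**What the plan says.** **SAP Section 6.** The only TEAE definition is worded for the current study. An event qualifies "if the AE begins on or after parent study Week 13 visit (Week 13 Day 3 visit for study 004", up to the 12-week post-treatment visit. It classifies by onset date alone. SAP 9.6.1 refers back to this definition and to no other.

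**Protocol Table 1, footnote 2.** On the gap before dosing starts in the extension: "A maximum duration of 3 weeks is permissible between the last ATYR1940 dose in the parent study (i.e., at Week 13". The parent Week 13 visit is thus the last parent dose. The ideal gap is 1 week, and more than 3 weeks is possible case by case.

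**Protocol 9.2.9.** The time limb reads: "a TEAE is defined as any AE that occurs after administration of the first dose of ATYR1940 through the 12-week posttreatment follow-up visit". It does not say which study's first dose is meant. A second limb, for worsening or newly related events, follows: "or any event that is present at baseline, but worsens in intensity or is subsequently considered drug-related by the Investigator". The same section promises that "Tabulations will be presented for safety data overall and separately for the parent and extension studies".

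**Protocol 8.5.10.2.** "All AEs will be collected and recorded in this study from the time of the first ATYR1940 dose in this study". It also assigns "AEs occurring through 30 days after the last study drug dose in the parent study" to parent-study reporting, and says that "all AEs that presented in the parent study that are ongoing at Week 1 in the current study will be recorded as such".

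**AE table shells.** All seven (14.2.1.1 to 14.2.1.7) have a block pooling parent and current studies. Six also have a current-study block; 14.2.1.4 shows only the pooled one.

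**SAP Section 1.1.** It lists the baseline change, schedule clarifications and the age range, and nothing about TEAEs.

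**The concern.** Long-term safety is part of the first study objective, and the current-study rows are where a reader looks for it. The AE shells have no parent-only block, so those rows are the only place where the tables separate the two studies. If they include events that began before any 006 infusion, and leave out older events that worsened during the extension, they do not describe what happened on extension treatment. This applies to the serious, related and withdrawal TEAE tables as well as the overall ones.

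The pooled block raises a different problem. Its TEAE rule has to be inferred, so two programmers could produce different counts from the same data.

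**Working it through.** **1. Start dates within the SAP.**
- TEAE for the current study: parent Week 13 visit (Section 6).
- Study day: first 006 infusion, with earlier dates negative (Section 6).
- Current-study treatment duration: first to last 006 dose (Listing 16.2.8 note; reported in Table 14.1.5).

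The TEAE window therefore opens one full gap before the other two clocks. For study 004 the anchor is Week 13 Day 3; that this is the last 004 dose is inferred from footnote 2, not stated separately.

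**2. Size of the early stretch.** The documents give no number of doses, so k is assumed. With k weekly doses and 12 weeks (84 days) of follow-up:
- Days from first 006 dose = 7(k − 1) + 84.
- SAP window = gap + that number. Share before the first 006 dose = gap / SAP window.

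| k | Days from first 006 dose | 7-day gap | 21-day gap |
|---|---|---|---|
| 48 | 413 | 7/420 = 1.7% | 21/434 = 4.8% |
| 24 | 245 | 7/252 = 2.8% | 21/266 = 7.9% |
| 12 | 161 | 7/168 = 4.2% | 21/182 = 11.5% |
| 1 | 84 | 7/91 = 7.7% | 21/105 = 20.0% |

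The last two rows represent early discontinuers. These are window-days, not event counts.

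**3. Tables affected.** 14.2.1.1, 14.2.1.2 and 14.2.1.7 show a current-study block; 14.2.1.3, 14.2.1.5 and 14.2.1.6 repeat the layout of 14.2.1.2. That is 6 of 7.

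**4. The omitted limb.** Protocol 9.2.9 adds events present at baseline that worsen or are later judged related. Protocol 9.2.1 uses parent baseline when the last parent dose was at most 4 weeks earlier, which covers 7- to 21-day gaps; SAP Sections 1.1 and 6 use parent baseline for everyone. An event present at parent baseline that worsens on the same record has an onset before Week 13, so the SAP rule misses it. If the worsening is entered as a new AE, which Protocol 8.5.10.1.1 allows for, the rule captures it.

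**5. Pooled block.** Section 6 restricts itself to the current study, so it supplies no pooled rule. SAP 1.0 says to read the plan together with the protocol, and the Protocol 9.2.9 definition fits this block. If a programmer instead applied Section 6 there, the parent days from Week 2 (first parent ATYR1940 dose, per the laboratory shell notes) to Week 13 would drop out: 11 × 7 = 77 days.
- k = 24: 77/(77 + 252) = 23.4%; 77/(77 + 266) = 22.4%.
- k = 48: 77/(77 + 420) = 15.5%; 77/(77 + 434) = 15.1%.

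**6. Imputation.** Appendix 2 sets an AE start to the first 006 dose when the date is wholly missing, when day and month are missing in the same year, or when only the day is missing in the same month. A parent event with such a date can become a current-study TEAE. The Appendix 2 note corrects this only when a complete stop date precedes the imputed start.

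**7. The protocol's 30-day rule.** It runs past the first 006 dose by 30 − 7 = 23 days or 30 − 21 = 9 days, so the protocol itself overlaps there.

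**The case against.** The case for leaving the plan alone is substantial. Because Protocol 9.2.9 names no study, a gap event already follows a first dose of ATYR1940 and is a TEAE overall; the SAP start only moves it between rows, and in the inclusive direction. Protocol 8.5.10.2 governs recording and reporting rather than classification, and followed strictly it would assign the first 9 to 23 days of 006 dosing to the parent study. Listing 16.2.9 gives start date, study day, study and TEAE flag for every event, so with up to 24 patients, dated gap events can be picked out by their negative study days. No hypothesis is tested, and Protocol 9.3 says that method changes will be documented in the study report.

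All of that stands as a limit on severity. It does not explain why the TEAE window should start earlier than study day and exposure, and the SAP gives no rationale.

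Two stronger readings are tempting. A reader might infer that 15% to 23% of the pooled window is lost; Section 6 is expressly limited to the current study, so that is only the result of misapplying it. A reader might also infer that restoring the protocol's limb would bring in every parent-study event that worsens during 006. For routine entrants the limb refers to parent baseline, so a worsening test at the first 006 dose would be a new rule.

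**Conclusion.** The concern holds as a misplacement of events and a set of unstated rules in descriptive tables; it falls between minor and should-fix. The current-study rows of six tables take in events from before any 006 dose, about 2% to 8% of window-days for 24 to 48 assumed weekly doses and gaps of 7 to 21 days, and more for early discontinuers or longer gaps. The omitted limb and the Appendix 2 effect cannot be sized from the documents. The missing pooled rule is an ambiguity with a sensible protocol fallback, not a demonstrated loss of data.

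The documents do not support saying that gap events are not TEAEs, or that the SAP start is wrong simply because it differs from Protocol 8.5.10.2. Protocol 8.5.10.3 and SAP 9.6.1 start AE collection at consent, whereas 8.5.10.2 starts it at the first 006 dose. That inconsistency needs its own reconciliation.

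**What to change.** Before database lock, amend the SAP as follows.

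- **Section 6, pooled block:** use the Protocol 9.2.9 definition, anchored at the first parent-study ATYR1940 infusion, with the worsening or newly-related limb judged against parent baseline.
- **Section 6, current-study block:** onset on or after the first 006 infusion through the 12-week follow-up. Events from parent Week 13 up to that infusion appear in the pooled block only.
- **Section 6, worsening during 006:** add events ongoing at the first 006 infusion that later worsen or become related. State this as a new SAP rule, identified from new AE records or by comparing parent and 006 records.
- **Duplicates:** the 30-day rule can put one event in both databases, so de-duplicate before counting.
- **Appendix 2:** do not impute a start to the first 006 dose when the event is already recorded in the parent study or its stop date shows earlier onset.
- **Section 1.1:** declare these departures.

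The cost is SAP wording, a change to the TEAE flag and date imputation in the AE analysis dataset, and a rerun of the seven AE tables and the listings that carry the flag. The worsening rule is limited by the data: Protocol 8.5.10.3 and Listing 16.2.9 show one intensity and one relationship per record, without dated changes. These SAP changes need no protocol amendment; the differing AE collection starts are reconciled separately.

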7.0 Interim Analyses

No interim analyses are planned for this study as the study is descriptive in nature and there are no inferential analyses. Data will be assessed at regular intervals by the sponsor, including planned safety evaluations performed by the ATYR1940 Data Monitoring Board (DMB) during the conduct of the study. Measures of PK, PD, and efficacy may also be assessed at regular intervals as appropriate.

8.0 Data Handling and Review

8.1 Visit Windows

Scheduled visits are as follows:

- Week 1, 2, 3, ... (Treatment Period – ATYR1940 dosing)
- 1-Week Post-treatment Follow-up (or early termination)
- 4-Week Post-treatment Follow-up (or early termination)
- 12-Week Post-treatment Follow-up (or early termination)

All data will be reported according to the nominal visit date for which it was recorded (i.e., no visit windows will be applied).

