6.4.2. Study Withdrawal Criteria

Patients will be informed that they have the right to withdraw from the study at any time for any reason, without prejudice to their medical care. The Investigator also has the right to withdraw patients from the study for any of the following reasons:

- Patient non-adherence to ATYR1940 or protocol requirements.
- Patient unwillingness to continue in the study.
- Any other reason, based upon the medical judgment of the Investigator.

The reason for study withdrawal is to be documented in the patient's source documents and electronic case report form (eCRF).

At the time of discontinuation from the study, patients are to have all the assessments planned for the 1- and 4-week posttreatment follow-up visits performed within 7-days after the last study drug dose, if feasible. (Note that some assessments are listed in both the 1- and 4-week follow-up visit; such assessments need only to be performed once at the time of discontinuation.)

Patients who are withdrawn from the study for any reason will not be replaced.

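### Early-termination pulmonary function tests, taken within 7 days of the last dose, are summarised as 4-week follow-up, and no rule keeps other early-termination values out of that row

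*SAP*

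**What the plan says.** Protocol 6.4.2 asks that patients discontinuing from the study have "all the assessments planned for the 1- and 4-week posttreatment follow-up visits performed within 7-days after the last study drug dose", where feasible. For items on both the 1- and 4-week lists, it adds that "such assessments need only to be performed once at the time of discontinuation". It does not mention the 12-week assessments.

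SAP 8.1 attaches early termination to all three follow-up visits: "1-Week Post-treatment Follow-up (or early termination"), "4-Week Post-treatment Follow-up (or early termination") and "12-Week Post-treatment Follow-up (or early termination"). It then states: "All data will be reported according to the nominal visit date for which it was recorded (i.e., no visit windows will be applied").

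SAP 6.0 says "Post baseline values for tabulations will exclude unscheduled visit values". Early termination appears in SAP 8.1 among the scheduled visits, so this exclusion does not remove it. None of the by-visit shells in SAP Appendix 5 has an early-termination row.

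**The concern.** The follow-up rows are where a reader looks for recovery or persistence of an effect after treatment stops. A row labelled 4-week should describe patients about four weeks after their last infusion. Under the plan it can mix those patients with others measured within one weekly dosing interval of the last dose. The tables would not reveal this. They show no time since last dose, and SAP 6.0 counts study day from the first infusion in this study.

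**Working it through.** The plan states no figure on this point, so there is nothing to reproduce. The check compares timings, traces each measure to its row, and shows how much of a row could be affected.

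**1. Timing, in days after the last dose** (protocol Table 1 windows and section 6.4.2)

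| Visit | Days |
|---|---|
| Early termination | 0 to 7 |
| 1-week (7 ± 3) | 4 to 10 |
| 4-week (28 ± 3) | 25 to 31 |
| 12-week (84 ± 5) | 79 to 89 |

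The smallest gap between an early-termination value and the 4-week window is 25 − 7 = 18 days. Against the nominal day 28, the value is 28 − 7 = 21 to 28 − 0 = 28 days early.

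**2. Which row each measure enters**

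- *Pulmonary function (FEV1, FVC, their ratio, total lung capacity, DLCO).* In protocol Table 1 and SAP 9.6.6.1 the only follow-up time point is the 4-week visit, and shell 14.2.5.1 has only that follow-up row. These tests are therefore part of the early-termination set, and the plan offers their values no other follow-up row. Actual values, change and percent change are all summarised there.
- *Laboratory tests, ECG, vital signs.* These are on both the 1- and 4-week lists and are done once at early termination. Their shells (14.2.2.1.1 and those built on it, 14.2.3.1, 14.2.4.1) have both rows. Nothing says which one the single value enters.
- *Manual muscle testing, Brooke and Vignos.* Their only follow-up row is the 1-week visit (shells 14.3.1 and 14.3.2). A value at day 0 to 7 is at most 4 days before that window opens, so little is wrong here.
- *Jo-1 antibody and ADA.* SAP 9.6.7 tabulates the maximum per patient, so there is no by-visit row.
- *MRI.* SAP 9.7.1 provides a listing only, and Listing 16.2.18 shows the scan date.

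**3. Share of a row.** The documents give no withdrawal rate. Assume that k of the planned maximum of 24 patients have early-termination values in the row and all others attend. The share is k/24:

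| k | Share |
|---|---|
| 1 | 4.2% |
| 2 | 8.3% |
| 4 | 16.7% |
| 6 | 25.0% |

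The row mean moves by that share of the true difference between early-termination and 4-week values, which the documents do not give. The tables are also split into three disease groups. With an assumed 8 patients per group, one such patient is 1/8 = 12.5% of a group's row.

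**4. Drug remaining at early termination.** The fraction left is 2^(−t/half-life). Protocol 2.3 gives a half-life of about 3 to 6 hours (single dose, healthy subjects). At day 1 this is 2^(−8) = 0.4% to 2^(−4) = 6%. At day 2 it is at most 2^(−8) = 0.4%. At day 7 it is at most 2^(−28), about 4 × 10⁻⁹.

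**The case against.** The best reply is that SAP 8.1 also attaches early termination to the 1-week visit, where day 0 to 7 is close to the right timing, and that values go under the visit for which they were recorded. For laboratory tests, ECG and vital signs this stands: they could equally enter the 1-week row, and the gap is a missing rule. It does not help pulmonary function, which has no 1-week row.

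The true timing can also be recovered. Listing 16.2.1 gives the last-dose date, and the laboratory and pulmonary function listings give assessment dates. That is correct, but the reader must link listings patient by patient to find what the table hides.

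A reader might infer more than the documents support, in four ways:

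- *That the 12-week row is contaminated by values 77 to 84 days early.* Protocol 6.4.2 calls only for the 1- and 4-week assessments at early termination. The 12-week label in SAP 8.1, and the MRI wording in SAP 4.2.1, are a mismatch with the protocol and with SAP 9.7.1.
- *That Jo-1, ADA and MRI follow-up summaries are distorted.* They have no by-visit summary.
- *That on-drug values are mixed with washout values.* With a 3 to 6 hour half-life, little circulating drug remains after day 1. The accurate contrast is within one dosing interval of the last dose against about four weeks after it.
- *That the affected patients are those with tolerability problems.* Protocol 6.4.1 has patients who stop drug but stay in the study return for the real 1-, 4- and 12-week visits, and requires this after a generalized infusion reaction or a raised Jo-1 level. The reasons in 6.4.2 are non-adherence, unwillingness and investigator judgment. Shell 14.1.2 does list adverse event and infusion-related reaction as reasons for leaving the study, so an informative pattern is possible but not shown.

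**Conclusion.** The point holds for the 4-week row. For pulmonary function, the plan as written places day 0 to 7 values in a row meant for day 25 to 31, an error of at least 18 days. For laboratory tests, ECG and vital signs the same misplacement is possible, because no mapping rule exists.

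The number of patients is unknown; the 4% to 25% range assumes 1 to 6 of 24 leave early and everyone else attends. Only patients who leave the study are affected, and only where the early-termination assessments are feasible. The conclusion also assumes that the database uses the visit names in SAP 8.1; the CRF is not among the documents.

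SAP 9.0 plans no hypothesis tests, so no error rate is at stake. What suffers is the summary of recovery after treatment in a long-term safety study. The repair is cheap enough that it should be made.

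**What to change.** In SAP 8.1, define early termination as its own visit. Report its values in a separate *Early termination* row of the by-visit tables, and keep them out of the 4-week and 12-week rows.

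A separate row is better than assigning values by days since last dose with the protocol Table 1 windows. The 1-week window opens at day 4, so values from days 0 to 3 would have no row.

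Reconcile the early-termination wording for the 12-week visit in SAP 8.1, and for MRI in SAP 4.2.1, with SAP 9.7.1 and protocol 6.4.2, neither of which calls for 12-week assessments at early termination.

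The cost is a short edit to the SAP text, one extra row in several shells, and slightly fewer patients in the 4-week row. No new data are needed.
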